6.4 Blinding

The trial is investigator-blinded.

As LEO 90100 and Daivobet® ointment are provided in different containers (LEO 90100 is in a can and Daivobet® ointment is in a tube), the subject will know which IMP he/she is receiving. To ensure that the investigator's assessment of efficacy and safety is not influenced or biased, the investigator will stay blinded throughout the trial. It is important that the investigator does not see or get information about which IMP the subject is receiving. The IMP will be handed out to the subjects by a designated person so the investigator will not know which IMP the subject has

received. Subjects will be instructed/reminded not to reveal the form of the IMP that they are dispensed to the investigator each time product is dispensed.

In addition, to minimise the risk of potential bias, a measure of artificial blinding will be implemented to preserve the integrity of the trial data. Detailed strategies on artificial blinding and a study team list specifying blinded and unblinded functions will be described in a blinding plan.

6.4.1 Breaking the Randomisation Code

Un-blinding of Individual Subject Treatment

Un-blinding of individual subject treatment is not considered necessary as the ingredients in the 2 IMPs are the same.

Un-blinding of the Clinical Trial

The clinical trial will be un-blinded when a final validated database has been produced, the statistical analysis specified in this protocol has been reviewed in relation to the blinded data actually obtained and the Statistical Analysis Plan (SAP) Update has been approved.

6.5 Treatment Compliance

Subjects will be provided with a paper diary to record adherence to the once daily treatment regimen during the treatment period. The diary should be returned to the site staff at the subsequent trial visit.

The investigator (or designee) should review the compliance data recorded by subjects in the paper diary before each visit. In case of non-compliance, the investigator should remind the subject of the importance of following the instructions given. Compliance/non-compliance and the reason for it must be recorded in the eCRF.

6.6 Dose Modification

Not applicable

6.7 Continued Access to Trial Treatment After the End of the Trial

After the end of the trial, subjects will be treated at the investigator's discretion or referred to other physician(s) according to standard practice.

6.8 Treatment of Overdose

For this study, any dose of LEO 90100 and Daivobet® ointment greater than 105 g within one week will be considered an overdose.

Overdose with calcipotriol may be associated with hypercalcaemia. Clinically important hypercalcaemia will be managed at the investigator's discretion with rehydration, bisphosphonate administration or according to local standard of care. Hypercalcaemia should rapidly subside when treatment is discontinued.

Overdose with corticosteroid containing products may result in suppression of adrenal function, which is usually reversible. In such cases, symptomatic treatment is indicated. In case of chronic toxicity, corticosteroid treatment must be discontinued gradually.

6.9 Prior and Concomitant Therapy

Any medication or vaccine (including over-the-counter or prescription medicines, recreational drugs, vitamins and/or herbal supplements) that the subject is receiving at the time of enrollment or receives during the trial must be recorded along with:

- Reason for use.
- Dates of administration including start and end dates.
- Dosage information including dose and frequency.
- The medical monitor should be contacted if there are any questions regarding concomitant or prior therapy.

Prior and Concomitant Medications Review

The investigator or qualified designee will review and record prior medication use taken by the subject within at least 16 weeks prior to treatment assignment or longer if required to washout other products per exclusion criterion 5.

The investigator or qualified designee will record medication, if any, taken by the subject during the study through the last visit. Concomitant medications will be recorded for 14 days after the last IMP administration (or longer if related to an SAE).

6.9.1 Concomitant Medication and Concurrent Procedures

Concomitant anti-psoriatic treatments allowed during the trial are listed in [Table 6-2](#).

Table 6–2 Permitted Concomitant Anti-psoriatic Treatment

Location	Permitted concomitant anti-psoriatic treatment
Scalp	Non-medicated and medicated shampoos/products except those that contain corticosteroids or vitamin D analogues (e.g., tar, salicylic acid, tazarotene, anthraline) are allowed.
Trunk/limbs	Bath oils and moisturising soaps are allowed. Unlimited use of emollients (except within 6 hours of clinic visits) is allowed. Emollients used should not contain alpha-hydroxy acids, beta-hydroxy acids or acetylic acid; emollients containing urea acid ($\leq 5\%$) are allowed.
Face and sensitive areas	Any topical treatments other than class 1–5* corticosteroids or vitamin D analogues (calcipotriol, calcitriol or tacalcitol) are allowed (e.g., topical calcineurin inhibitors). Topical use of mild corticosteroids (class 6–7)* is allowed, but should be for short term use and be minimised to the largest possible extent. Unlimited use of emollients is allowed. Bath oils and moisturising soaps are allowed.

* Corticosteroid classified by World Health Organization (WHO) model prescribing information: drugs used in skin diseases, 1997¹⁹.

Note: Sensitive areas refer to armpits, groin, under the breasts and in other skin folds around the genitals and buttocks.

Any medication or vaccine that the subject receives and any medical procedure the subject undergoes, from screening through follow-up, must be recorded in the subject's medical record and the eCRF.

6.9.2 Rescue Treatment

If medically necessary (i.e., to control intolerable psoriatic symptoms), rescue treatment for stable plaque psoriasis can be initiated to trial subjects at the discretion of the investigator. If possible, investigators should attempt to limit the first step of rescue treatment to topical treatments. Before the initiation of rescue treatment, investigators should make every attempt to conduct efficacy and safety assessments (for example, disease severity scores [PASI and sPGA] and safety labs). Unscheduled visit(s) may be used for this purpose, if necessary.

The investigator is responsible for the rescue treatment oversight and duration as well as switching and escalating to another rescue therapy, when appropriate. The investigator should consider if discontinuation of IMP is necessary depending on the type of rescue medication and the severity of the subject's symptoms (see Section 7, discontinuation criteria).

The use of any rescue treatment must be recorded in the eCRF (refer to Section 7).

6.9.3 Prohibited Medication and Procedures

Prohibited medications and procedures during the trial are listed in [Table 6–3](#). Details regarding prohibited medications and procedures prior to screening and during washout are also described in Section [5.3](#).

In case any prohibited medication is used during the trial, they must be recorded as concomitant medication.

Table 6–3 Prohibited Medications and Procedures

Medication or procedure	Prohibited from	Prohibited to
Systemic treatment with biological therapies (marketed and not marketed), with a possible effect on plaque psoriasis	Etanercept: 4 weeks prior to treatment assignment.	End-of-trial (Week 6)
	Adalimumab, Infliximab or Brodalumab: 8 weeks prior to treatment assignment.	End-of-trial (Week 6)
	Ustekinumab: 16 weeks prior to treatment assignment.	End-of-trial (Week 6)
	Secukinumab: 12 weeks prior to treatment assignment.	End-of-trial (Week 6)
	Other products: within 4 weeks/5 half-lives prior to treatment assignment (whichever is longer).	End-of-trial (Week 6)
Systemic treatment with therapies other than biologicals with a possible effect on plaque psoriasis (e.g., corticosteroids, retinoids, methotrexate, ciclosporin, other immunosuppressants and traditional Chinese medicine)	4 weeks prior to treatment assignment.	End-of-trial (Week 6)
Systemic treatment with Apremilast	4 weeks prior to treatment assignment.	End-of-trial (Week 6)
Use of non-marketed/other IMPs	4 weeks or 5 half-lives (whichever is longer) prior to treatment assignment.	End-of-trial (Week 6)
PUVA therapy	4 weeks prior to treatment assignment.	End-of-trial (Week 6)
UVB therapy	2 weeks prior to treatment assignment.	End-of-trial (Week 6)

Medication or procedure	Prohibited from	Prohibited to
Any topical treatment including corticosteroids (except for emollients, non-steroid medicated shampoos and low potency corticosteroids on sensitive areas)	2 weeks prior to treatment assignment. On areas treated with the IMP, emollients should not be used within 6 hours of clinic visits.	End-of-trial (Week 6)
Initiation of or changes to concomitant medication that could affect plaque psoriasis (e.g., beta-blockers, lithium, anti-malaria drugs, ACE inhibitors)	Treatment assignment.	End-of-trial (Week 6)
Vitamin D supplements > 400 IU/day, (note: stable dose of vitamin D supplements ≤ 400 IU/day is permitted)	Treatment assignment.	End-of-trial (Week 6)

Abbreviations: ACE=angiotensin-converting-enzyme; IMP=investigational medicinal product; PUVA=psoralen combined with ultraviolet A therapy; UVB=ultraviolet B.

7 Discontinuation of Trial Treatment and Subject Discontinuation

A subject may withdraw from the trial (prior to first dose or during the treatment period) or permanently discontinue IMP at any time if the subject, the investigator or the medical monitor of the designated CRO considers that it is not in the subject's best interest to continue. The decision made by the designated CRO will need to be confirmed by LEO Pharma A/S.

Subjects who withdraw from the trial and subjects who permanently discontinue IMP will not be replaced.

Discontinuation of specific sites or of the study as a whole are handled as part of the appendix on Governance, [Appendix 1](#), Section 10.1.8.

7.1 Discontinuation of Trial Treatment

It may be necessary for a subject to permanently discontinue IMP. If IMP is permanently discontinued, the subject should, if at all possible, remain in the study and attend an early termination visit and a follow-up visit 2 weeks after the last IMP administration. See the SoA ([Table 1–1](#)) for data to be collected at the time of IMP discontinuation and follow-up and for any further evaluations that need to be completed.

IMP must be discontinued permanently in case of the following:

- An AE that, in the opinion of the investigator or medical monitor of the designated CRO, contraindicates further dosing. The decision made by the designated CRO will need to be confirmed by LEO Pharma A/S;
- Evidence of pregnancy;
- Subject decides to discontinue voluntarily;
- Lack of efficacy defined as at least a **CCI** [REDACTED] in mPASI score from baseline until Week 2 or unscheduled visits thereafter and where the investigator sees a need for rescue therapy.

End-of-treatment Form

An end-of-treatment form will be completed in the eCRF for all subjects exposed to IMP when they have had their last IMP administration. This form will also be completed for subjects who permanently discontinue IMP prior to Week 4 and subjects who withdraw from the trial, unless they were never exposed to IMP (see [Table 1–1](#) for early termination assessments).

The date and time of last IMP administration and time of permanent discontinuation of IMP will be recorded on the end-of-treatment form. It will also be recorded if the subject completed the IMP treatment (i.e., did not discontinue IMP prior to Week 4). If not, the primary reason for permanent IMP discontinuation must be recorded in the medical records and on the end-of-treatment form in the eCRF where the following options are available:

- AE;
- Death;
- Lost to follow-up;
- Pregnancy;
- Withdrawal by subject;
- Lack of efficacy;
- Pandemic restrictions as defined in [Section 9.3.5.1](#);
- Other.

If ‘AE’ is selected, the AE in question will be linked to the IMP discontinuation. If ‘other’ is selected as a reason, a specification must be provided in the eCRF.

It will also be recorded whether the IMP discontinuation was related to the COVID-19 pandemic to support the statistical analysis.

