- 3 Subjects who permanently discontinue IMP or withdraw from the trial will be asked to come for the primary endpoint visit and will be followed up (Section [7.1](#)).
- 4 The ICF must be signed prior to performing any protocol-related procedures, including but not limited to screening evaluations and washout of prohibited medications. Screening evaluations can be either on the same date the ICF was signed or at a later date.
- 5 In case medical history is incomplete at screening visit, missing data will be retrieved at Day 1 (baseline).
- 6 To supplement the compliance check made at Visits 3 and 4, a subject diary should be completed daily during the treatment period.
- 7 Treatment compliance includes recording the number of applications missed by each subject (Section [6.5](#)).
- 8 The body areas to be assessed are the trunk (including the neck) and the limbs, i.e., arms (including hands) and legs (including feet and buttocks). The face, scalp, genitals and skin folds (i.e., the axillae, the inguinal folds, the inter-gluteal folds and the infra-mammary folds) are not to be treated with the IMP or assessed as part of the efficacy analysis.
- 9 An end-of-treatment form (Section [7.1](#)) and end-of-trial form (Section [4.4](#)) must be completed in the eCRF for all subjects assigned to treatment.

2 Introduction

LEO 90100 (Enstilar® Foam) is a fixed combination product containing calcipotriol monohydrate, a vitamin D analogue, and betamethasone dipropionate, a potent steroid that is approved for topical treatment of stable plaque psoriasis in many countries.

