4.1 Overall Design

This phase 3, randomised, prospective, investigator-blinded, active-controlled, parallel group, multicentre trial will evaluate the efficacy and safety of 4 weeks treatment with LEO 90100 compared with Daivobet® ointment in native Chinese subjects (aged ≥ 18 years) with at least mild stable plaque psoriasis.

600 trial subjects are planned to be randomised in a 1:1 ratio to either LEO 90100 or Daivobet® ointment treatment. Randomisation will be stratified by Physician's Global Assessment of disease severity (PGA) at baseline (mild [PGA=2], moderate [PGA=3] or severe [PGA=4]).

For each subject, the trial will last 6 weeks to 10 weeks, including:

- A washout/screening period up to 4 weeks (at least 1 visit);
- A treatment period up to 4 weeks (3 visits);
- A safety follow-up period of 2 weeks (1 visit for all subjects 2 weeks after the last IMP administration).

The subjects will provide written consent according to national laws and regulations before any trial-related activities are carried out.

Washout/Screening Period

For subjects who have been receiving prohibited medications (see Section 6.9) prior to screening, the screening period may be extended up to 4 weeks to ensure they complete the required washout period before they start receiving the IMP. On completion of the washout period, confirmation of the subject's ongoing eligibility for the trial will be made at Day 1 (baseline). However, if no washout is needed the subject will enter Day 1 (baseline) directly.

Treatment Period

The treatment period will last for up to 4 weeks and includes 3 visits: Visit 2 (Day 1), Visit 3 (Week 2) and Visit 4 (Week 4). The start of IMP treatment will be at Day 1 and this visit will be considered as baseline. The first application of the IMP will be made at site under supervision and instruction of an un-blinded member of the trial staff (not the investigator, as this is an investigator-blinded trial) at the Day 1 visit. The subjects also have the option to apply the first IMP at home after the instruction has been given at the site. Refer to Section 6.1 for further details on the treatment principles applied.

Follow-up Period

The follow-up visit (Visit 5) will be performed at Week 6, which is 2 weeks after the last visit in the treatment period.

The trial design is illustrated in [Figure 1–1](#) and visit schedule is provided in [Table 1–1](#).

Refer to Section [10.5](#) for the COVID-19 pandemic contingency plan.

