4.4 End-of-Trial Definition

The end of the trial is defined as the date of the last visit of the last subject in the trial.

A subject is considered to have completed the trial if he/she has completed all periods of the trial including the last follow-up visit.

End-of-trial Form

An end-of-trial form must be completed in the electronic case report form (eCRF) for all subjects assigned to treatment when they have had their last visit (that is, the follow-up visit at Week 6 or early termination visit). The following data will be collected:

- Date of last contact.
- Did the subject complete the trial?
- Primary reason for not completing the trial based on the following categories: death, AE, lack of efficacy, lost to follow-up, withdrawal by subject, screen failure (failure to meet eligibility criteria) or other.
- Whether the reason for not completing the trial was related to COVID-19.

If ‘AE’ is selected, the AE in question will be linked to the non-completion of the trial. If ‘other’ is selected as a reason, a specification must be provided in the eCRF. If ‘withdrawal by subject’ is selected, it will be recorded whether the subject withdrew informed consent or not.

For end-of-treatment form, please referred to Section [7.1](#).

5 Trial Population

Prospective approval of protocol deviations to eligibility criteria, also known as protocol waivers or exemptions, is not permitted.

The trial population will consist of subjects who are native Chinese subjects aged ≥ 18 years with stable plaque psoriasis. Subjects must be able to provide written consent and meet all the inclusion criteria and none of the exclusion criteria.

It will be recorded in the eCRF if the subject has met all the inclusion criteria and none of the exclusion criteria.

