7.3 Loss to Follow-Up

A subject will be considered lost to follow-up if the subject repeatedly fails to return for scheduled visits and are unable to be contacted by the trial site.

The following actions must be taken if a subject fails to return to the clinic for a required study visit:

- The site must attempt to contact the subject and reschedule the missed visit as soon as possible (and within the visit window, where one is defined), counsel the subject on the importance of maintaining the assigned visit schedule, and ascertain whether the subject wishes to and/or should continue in the trial.
- In cases in which the subject is deemed lost to follow-up, the investigator or designee must make every effort to regain contact with the subject (where possible, 3 telephone calls and, if necessary, a certified letter to the subject's last known mailing address or local equivalent methods). These contact attempts should be documented in the subject's medical record/eCRF.
- Should the subject continue to be unreachable, the subject will be considered to have withdrawn from the study.

8 Study Assessments and Procedures

Study procedures and their timing are summarised in the SoA (Table 1–1). Protocol waivers or exemptions are not allowed. The IMP will be administered after subject and investigator assessments.

Trial subjects will be under careful supervision by the principal investigator who must be a dermatologist. Investigators must be physicians who are experienced in treating psoriasis, have documented experience and have received the training for the use of the assessments required by the protocol.

AEs must be assessed by a physician (Section 8.4).

Immediate safety concerns should be discussed with LEO Pharma A/S immediately upon occurrence or awareness to determine if the subject should continue or discontinue the IMP.

Adherence to the study design requirements, including those specified in the SoA, is essential and required for study conduct.

All screening evaluations must be completed and reviewed to confirm that potential subjects meet all eligibility criteria. The investigator will maintain a screening log to record details of all subjects screened and to confirm eligibility or record reasons for screening failure, as applicable.

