8.4.1 Time Period and Frequency for Collecting AE and SAE Information

All AEs and SAEs will be collected from the signing of informed consent form (ICF) until the end-of-trial (defined as attending the last visit in the trial [the early termination visit or the last follow-up visit (Visit 5), whichever comes last]), at the timepoints specified in the SoA ([Table 1–1](#)).

It will be recorded in the eCRF if the AE started prior to first IMP administration.

All SAEs will be recorded and reported to LEO Pharma A/S immediately without undue delay but no later than within 24 hours of awareness, as indicated in [Appendix 3](#). The investigator will submit any updated SAE data to LEO Pharma A/S within 24 hours of it being available.

Investigators are not obliged to actively seek information on AEs or SAEs after the conclusion of trial participation. However, if the investigator learns of any SAE, including a death, at any time after a subject has been discharged from the trial, and the investigator considers the event to be reasonably related to the IMP or trial participation, the investigator must promptly notify LEO Pharma A/S.

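### Visit instructions for subjects who stop IMP need reconciling, and the SAP's nominal-visit rule could replace an observed in-window score with an imputed one in supportive analyses

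*Protocol*

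**What the plan says.** **Visits after stopping IMP.** Protocol 7.1 asks these subjects to remain in the study if at all possible and to "attend an early termination visit and a follow-up visit 2 weeks after the last IMP administration". It then refers to the SoA, among other things "for any further evaluations that need to be completed". SoA footnote 3, attached to the early termination column and repeated in SAP Appendix 4, says that subjects who discontinue IMP or withdraw "will be asked to come for the primary endpoint visit" and cites 7.1. Protocol Section 8 says that adherence to the design requirements, "including those specified in the SoA, is essential and required for study conduct".

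**Follow-up timing.** Protocol 4.1 describes the safety follow-up as "1 visit for all subjects 2 weeks after the last IMP administration". Under its follow-up heading it says: "The follow-up visit (Visit 5) will be performed at Week 6". The SoA puts Visit 5 at Day 43 ±3. The SoA has PGA and mPASI at Weeks 2 and 4 and at early termination, but not at follow-up.

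**Analysis.** SAP 6.3.1.1 uses the nominal visit recorded in EDC and excludes re-mapping. For discontinuation unrelated to the pandemic, SAP Table 4-1 (Protocol Table 9-2) sets non-response in the primary binary estimand whether or not Week 4 was observed. The secondary binary and continuous estimands use Week 4 as observed, and otherwise multiple imputation under MAR within arm. The sensitivity analysis of the primary estimand uses observed Week 4 data from Daivobet-arm discontinuers and imputes that arm's missing data.

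**The concern.** A treatment-policy estimand is only as good as the data collected after treatment stops. Here the section on discontinuation does not name the visit that supplies those data, and the footnote that does name it points back to that section. A site working mainly from 7.1 could treat the early termination visit as the last efficacy assessment.

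The SAP adds a second, narrower route. A score taken inside the Week 4 window but labelled early termination has no place in the Week 4 analysis. It cannot inform the imputation either, because the model in SAP 6.3.3 holds only Week 2, Week 4, PGA stratum and baseline. The imputation has no indicator for having stopped IMP. These subjects would therefore be given values modelled on others in their arm, even though lack of efficacy with a need for rescue is one of the reasons for stopping in 7.1.

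At stake is how far the supportive results rest on observed data.

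**Working it through.** The plan gives no figure on this point: no discontinuation rate, no response rate after stopping, and no expected share without Week 4 data. The check is therefore day arithmetic, a trace through the analysis rules, and an illustration under stated assumptions.

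**1. Timing.** Inputs: Visit 4 is Day 29 ±3, so Days 26-32. Visit 5 is Day 43 ±3, so Days 40-46 (SoA). With the last dose on Day L, follow-up under 7.1 falls on Day L + 14.

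| Last dose (Day L) | Follow-up (Day L + 14) | Visit 4 window, Days 26-32 | Visit 5 window, Days 40-46 |
|---|---|---|---|
| 1-11 | 15-25 | before | before |
| 12-18 | 26-32 | inside | before |
| 19-25 | 33-39 | after | before |
| 26-29 | 40-43 | after | inside |

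Both timings hold only if L + 14 ≥ 40, that is L ≥ 26. The gap from nominal Day 43 is 43 - (L + 14) = 29 - L days: 21 days at L = 8, 15 at L = 14 and 1 at L = 28. The documents attach ±3 days to Day 43 only. If the last-dose timing were also allowed +3 days, the condition would be L + 17 ≥ 40, that is L ≥ 23.

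**2. Does follow-up timing affect Week 4 efficacy data?** No. For L = 12-18 the follow-up falls inside the Visit 4 window, but the follow-up column has no PGA or mPASI. Moving that visit neither supplies nor removes a Week 4 score.

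**3. The nominal-visit rule.** Take a discontinuer scored on any of Days 26-32 at a visit recorded in EDC as early termination, with no Visit 4 record.
- SAP 6.3.1.1: Week 4 is missing.
- Primary binary estimand: non-response, the same as if Week 4 were observed. PGA, mPASI-75 and mPASI-90 in the confirmatory hierarchy do not change.
- Secondary binary and continuous estimands, by Table 4-1: imputed, where a Visit 4 label would have meant used as observed.
- Sensitivity analysis, Daivobet arm: the same switch from observed to imputed.

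The predictors are PGA stratum, baseline score (for endpoints other than PGA) and Week 2.

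**4. A discrepancy that bears on step 3.** The narrative on the secondary estimand (Protocol 9.3.5.2, SAP 4.1.5.2) lists only pandemic-related cases for imputation. Tables 9-2 and 4-1 also impute missing data unrelated to the pandemic. SAP 4.1.5.1 reports that no pandemic-related discontinuation or missing data occurred. Read alone, the narrative would then leave nobody to impute. Step 3 follows the tables.

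**5. Illustration of size (all inputs assumed).** The shift in an arm's response rate is s × m × (q - r). Here s is the share discontinuing, m the share of those without a nominal Week 4 score, q their mean imputed response and r the response that would have been observed. Take q - r from -20 to +40 points.
- s = 2% (300 × 0.02 = 6 subjects), m = 50%: 0.02 × 0.5 × (-20 to +40) = -0.2 to +0.4 points.
- s = 5% (15 subjects), m = 50%: -0.5 to +1.0 points.
- s = 10% (30 subjects), m = 50%: -1.0 to +2.0 points.
- s = 10%, m = 100%: -2.0 to +4.0 points; m = 25%: -0.5 to +1.0 points.

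The effect on the odds ratio depends on how the shift differs between arms. For the mapping rule alone, m counts only subjects with an in-window score recorded as early termination.

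**The case against.** The best answer is that Week 4 collection is already asked for. Section 7.1 sends the site to the SoA, footnote 3 there names the primary endpoint visit, and Section 8 requires the SoA to be followed. A site that collects nothing at Week 4 has overlooked the pointer in 7.1 itself. This stands. A reader might infer that the protocol fails to collect Week 4 data after discontinuation, and the documents do not support that. What is left is an incomplete cross-reference that sites could apply differently.

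A reader might also infer that the double timing of follow-up causes Week 4 data to be lost, or that the trial would end before the Week 4 visit for every last dose up to Day 14. Neither holds. Follow-up carries no efficacy score. For last doses on Days 12-14 it falls on Days 26-28, inside the Visit 4 window. Allowing +3 days, only last doses up to Day 8 put follow-up before the window for certain (8 + 17 = 25). Section 8.4.1 defines the end of trial by "the early termination visit or the last follow-up visit (Visit 5), whichever comes last", and the SoA puts Visit 5 at Day 43. Section 4.4 words the last visit differently but compatibly.

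Finally, nominal-visit analysis is a clear pre-specified rule, and keeping earlier early termination scores out of Week 4 is sensible. The documents do not show how the eCRF would label an in-window visit, and under footnote 3 it might be entered as Visit 4. That limits how often the rule would cost data. It does not justify imputing a value that was observed in the window.

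**Conclusion.** The point holds as a low-cost improvement to supportive analyses. Three things are established from the text: 7.1 and footnote 3 name different visits for the same subjects, although they can be read together; the two follow-up timings cannot both be met for a last dose before Day 26, counting exactly 14 days; and SAP 6.3.1.1 as written would exclude a Days 26-32 early termination score from Week 4 when no Visit 4 record exists.

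A reader might take this as a threat to the primary result. It is not one, because discontinuation unrelated to the pandemic sets non-response in the primary estimand whatever was observed. The exposed analyses are the secondary binary estimand, the continuous estimand and the Daivobet-arm sensitivity analysis.

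The documents fix neither the size nor the direction. The illustrated shifts rest wholly on assumed inputs and are not bounds. That missing Week 4 values are imputed at all rests on the tables rather than the narrower narrative.

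**What to change.** 1. **Protocol.** Reconcile 7.1 with SoA footnote 3, so that it is explicit which visits and which PGA and mPASI assessments apply to subjects who stop IMP and remain in the study. Reconcile the follow-up timing in 4.1, 7.1 and the SoA. Which timing applies is for the sponsor to settle.
2. **SAP 6.3.1.1.** Add a fallback: when no nominal Visit 4 value exists, an early termination PGA or mPASI taken on Days 26-32 is assigned to Week 4 for the treatment-policy and sensitivity analyses. Settle this before unblinding.
3. **SAP 4.1.5.2 and Protocol 9.3.5.2.** Align the secondary-estimand narrative with Tables 4-1 and 9-2 on imputing missing data unrelated to the pandemic. Report, per arm, the number of discontinuers with observed and with imputed Week 4 data, next to the planned summary of intercurrent events.

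The cost is wording, minor programming and one table line. The mapping rule rescues only in-window scores recorded as early termination. The protocol wording helps only while subjects are still on study. SAP 2.0 already reports on pandemic-related events among all subjects before database lock, so items 2 and 3 may be the only ones that can still take effect.
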